### **Introduction**

Anterior cruciate ligament (ACL) injury is a very common injury for adolescents and young adults with over 200,000 ACL injuries reported in the United States each year [1]. The standard treatment for this injury includes ACL reconstruction surgery and physical therapy. Rehabilitation of this surgery requires that adequate quadriceps rehabilitation is important for full return function and activity. The role of quadriceps strength recovery after ACL reconstruction has been well studied and is associated with return to play times, knee kinematics and patient reported outcomes [2]. Paterno et al. reported that patients with greater fear on Tampa Scale of Kinesiophobia (TSK-11) were six times more likely to have a quadriceps LSI of less than 90% supporting the role of adequate quadriceps strength in reduction of risk of sustaining a contralateral ACL injury or re-injury [3]. Ithurburn additionally reported that athletes who demonstrated quadriceps strength asymmetry at time of return to sport (RTS) were likely to demonstrate lower knee related function [4].

### **Background**

Exercise training with blood flow restriction (BFR) is a technique increasingly used in physical therapy and rehabilitation settings as an alternative to heavy load resistance exercise, and has increased in popularity in clinical and healthy populations over the last two decades. Exercise is completed in conjunction with a surgical grade pneumatic cuff or tourniquet. Evidence has suggested that BFR assists with muscle hypertrophy, as well lower extremity and upper extremity strength in several populations including athletes, post-operation rehabilitation [5], and the elderly [6]. The clinical value of this technique has been posed to allow increased muscle adaptation and hypertrophy under low loads and intensity that could heretofore only be accomplished with impact activities and more intense training protocols. This is very attractive in a population of early post-operative patients who are not able to engage in this level of activity.

Following ACL reconstruction patients have demonstrated persistent quadriceps strength deficits during and after rehabilitation. Despite there being special attention paid to restoring quadriceps and hamstring strength to pre-operative levels, there is a need for additional intervention. The utilization of BFR in conjunction with current rehabilitation standards of care has shown potential [7]. A meta-analysis completed in 2017 comparing BFR training on musculoskeletal rehabilitation versus traditional low load training, and reported that low load BFR training to be more effective in helping patients regain strength than traditional low load strength training [7]. In a 2018 review of BFR during ACL rehabilitation the authors state the use of BFR as a safe alternative to heavy loads reducing the risk of damage to the graft, cartilage, and meniscus [8]. Current ACSM guidelines for resistance training recommend 70% of a single maximum repetition (RM) to elicit strength and hypertrophy adaptations [9]. BFR provides an alternative to heavy load resistance training due to the light loads prescribed to help reduce mechanical stress on the post-operative knee.

Connecticut Children's Sports Physical Therapy and Elite Sports Medicine have a long relationship of working collectively with the management of patients with ACL tears both surgically and with rehabilitation post-surgically. The current standard of care for the rehabilitation of ACL injuries includes several interventions and the process can last up to 12 months. The early phases of rehabilitation include the use of therapeutic exercise, manual therapy and modalities to help reduce pain, normalize range of motion and gait. In the later phases, a progressive lower extremity strengthening program is completed, in addition to plyometric and jump training. Finally, Standardized strength assessments at 3 months' post-operative, and return to sport test between 6 and 9 months are used to help physical therapists and surgeons in clinical decision making for progression with functional and recreational activities. Since early 2019, BFR training has been implemented consistently for post-operative patients at Connecticut Children's Sports Physical Therapy that have undergone ACL reconstruction, as well as patellar and shoulder stabilization procedures.

While there are a number studies that have reported on the use of BFR in the adult population [14], there is limited information about the use of BFR in the adolescent population. This study aims to

evaluate the use of BFR training in conjunction with traditional ACL reconstruction rehabilitation in adolescents.

## **Previous Work**

Until recently, previous studies have examined the use of BFR with respect to muscular strength, endurance and hypertrophy. With the rise in popularity of BFR, there has been increased attention to overall safety issues of training with BFR. The potential risks to the cardiovascular system that have been considered are increased blood pressure responses, thrombolytic events and damage to the vascular system [10].Despite these concerns, there have been several extensive reviews published demonstrating that the side effects are minimal [10, 11, 12], and that training with BFR and when compared with traditional methods shows no greater risk [13]. Additionally, a closer look at the literature has demonstrated that the use of BFR has shown significant strength adaptations in multiple patient populations:

- A 2017 study showed a 2-fold improvement in extension and flexion strength with the use of BFR in patients after knee arthroscopy [15].
- Patients with patellofemoral pain had greater improvements in knee extension strength following the use of BFR training [14].
- A 2003 study demonstrated improved quadriceps strength with BFR training in patients after ACL reconstruction [16].
- Greater improvements in thigh circumference as opposed to a standard group [17].

## **Research Question:**

The purpose of this study is to evaluate the addition of BFR-based exercise to traditional methods of physical therapy. Does the use of BFR-based exercise improve strength, hypertrophy, functional and patient reported outcomes after ACL Reconstruction in the adolescent population?

## Purpose of the Research, Specific Aims and Hypotheses

The purpose of this study is to determine the safety and efficacy regarding the addition of BFR-based exercise to traditional methods of physical therapy in the adolescent, post-surgical population.

## Primary aims:

- 1. To determine the relationship between adjunct BFR training during post-surgical rehabilitation and isometric and isokinetic lower extremity strength measures (HUMAC isokinetic dynamometer).
  - a. We hypothesize that there will be a positive association between BFR training and isometric and isokinetic lower extremity strength
- 2. To determine the impact of adding BFR training during post-surgical rehabilitation on functional outcomes.
  - a. We hypothesize that BFR training will improve scores on lower extremity functional tests when compared to a control group.

### Secondary aim:

- 1. To determine the impact of adding BFR training during post-surgical rehabilitation on patient reported outcomes.
  - a. We hypothesize that BFR training will show greater patient reported outcome scores on the post-op when compared to a control group.
- 2. To determine the impact of adding BFR training during post-surgical rehabilitation on hypertrophy and mid-thigh circumference.
  - a. We hypothesize that BFR training will demonstrate significant increased mid-thigh circumference over measured time points.
- 3. To determine and record patient tolerance and reported side effects and to BFR training during postsurgical rehabilitation.
  - a. We hypothesize that patient tolerance to BFR will be consistent with previously published literature.

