## 4.

## A) Pre-operative visit

- a. Isometric knee extension at 60 degrees on involved and involved side.
  - i. Quadriceps deficit= 100- (Knee extension peak torque involved/knee extension peak torque uninvolved)
- b. Isometric knee flexion at 60 degrees on involved and uninvolved side
  - i. Hamstring Deficit= 100- (Knee flexion peak torque involved/knee flexion peak torque uninvolved)
- c. Isometric hip extension at 60 degrees on involved and uninvolved side
  - i. Hip extension deficit= 100- (Hip extension peak torque involved/hip extension peak torque uninvolved)
- d. Quad hypertrophy will be measured by thigh circumference measurement.
  - i. Measured at 10cm above the superior pole of the patella bilaterally

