## Data Analysis:

The endpoint of this study is when data is collected and analyzed from 20 patients who have completed a one year follow up from date of surgery.

Data will be collected on all patients who meet the inclusion criteria for this study and have agreed to participate through the consenting process. Descriptive statistics will be completed to help gain an overall understanding of the data for the effect of BFR training on lower extremity strength, mid-thigh circumference and outcome measures. T-tests between strength and outcome variables for the BFR and non-BFR group to test if there are differences between the two groups. Correlation tests will be used to determine association between lower extremity strength and BFR training. Corrections will be made for multiple comparisons.

We will be entering into a Data Use Agreement with University of Connecticut (UCONN) for assistance with data analysis and interpretation as well as statistical analysis. All data sharing procedures will be in accordance with Connecticut Children's policy. All data will be de-identified prior to sharing to assure patient's confidentiality. The UCONN collaborator is not engaged in human subject research (no access to identifiers) and will obtain an independent determination from the UCONN IRB.

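### Secondary hypothesis 2a is worded as a rise in thigh circumference over time with no control group, so it does not match the aim of estimating what adding BFR does

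*Combined protocol and SAP*

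**What the plan says.** Under Secondary aim, item 2, the stated aim is "To determine the impact of adding BFR training during post-surgical rehabilitation on hypertrophy and mid-thigh circumference". The hypothesis attached to it, 2a, is "We hypothesize that BFR training will demonstrate significant increased mid-thigh circumference over measured time points".

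The two other hypotheses that sit under an aim about the impact of adding BFR both name a comparator. Primary hypothesis 2a reads "We hypothesize that BFR training will improve scores on lower extremity functional tests when compared to a control group", and secondary hypothesis 1a reads "We hypothesize that BFR training will show greater patient reported outcome scores on the post-op when compared to a control group".

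On measurement, the pre-operative visit section states "Quad hypertrophy will be measured by thigh circumference measurement" and "Measured at 10cm above the superior pole of the patella bilaterally". The same measurement is repeated at 3 months and at return to sport testing. No side-to-side index is defined for circumference, although deficits or differences are defined for strength, reach and hop tests.

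The Data Analysis section first plans descriptive statistics, naming strength, mid-thigh circumference and outcome measures as three items. It then plans "T-tests between strength and outcome variables for the BFR and non-BFR group to test if there are differences between the two groups", followed by correlation tests and a correction for multiple comparisons. It mentions no paired or repeated-measures test.

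The numbered items on controls, after the 12-month testing item, say that prospective controls supply the same data points as the BFR group. For retrospective controls they name two patient-reported scores and the 3-month and 6-month-plus assessments. No pre-operative assessment is named for them.

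**The concern.** The aim calls for a between-group contrast. The hypothesis can be met by a change within the BFR group alone. These are different questions, and only the first concerns BFR.

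All patients follow a rehabilitation protocol that includes progressive strengthening, and the age range is 12 to 18 years at surgery. Thigh circumference can therefore rise between two visits, for example from 3 months to return to sport, with no contribution from BFR. A result that meets 2a as worded could then be read as evidence of BFR-induced hypertrophy even if controls gained just as much. Conversely, if circumference falls after surgery, a comparison of pre-operative with 3 months could fail 2a even if BFR limited the loss. The hypothesis does not say which visits, or which limb, count.

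**Working it through.** **Step 1. Set the hypotheses side by side.**

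| Item | What the aim asks | Comparator in the hypothesis |
|---|---|---|
| Primary 2 / 2a | Impact of adding BFR on function | Control group |
| Secondary 1 / 1a | Impact of adding BFR on patient-reported outcomes | Control group |
| Secondary 2 / 2a | Impact of adding BFR on circumference | None; change over time points |

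The three aims have the same form. Only the circumference hypothesis drops the control group.

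**Step 2. See whether the analysis section supplies the comparator.** The descriptive sentence lists circumference separately from outcome measures, and the t-test sentence covers strength and outcome variables only. Read strictly, circumference is described but not compared. Read broadly, it is one of the outcome variables. The text does not settle this. Under either reading, no test of change over time is specified for 2a.

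**Step 3. Illustrate what a within-group reading could do.** The documents give no alpha, SD or expected change for circumference, so there is no stated figure to reproduce. Assumptions: the BFR effect is zero; both groups rise by the same amount d, in SDs of the individual change score; the test is two-sided at 0.05; there is no multiplicity correction. From the documents: 33 BFR patients (Study Design), and 20 patients as the number that triggers the analysis (Data Analysis).

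For a paired t-test in n patients, the noncentrality is d × √n, and the chance of a significant rise is 1 − F(t₀.₉₇₅; n − 1, d√n), where F is the noncentral t distribution function.

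| d | n = 33: d√n | Chance of significant rise | n = 20: d√n | Chance of significant rise |
|---|---|---|---|---|
| 0 | 0 | 0.025 | 0 | 0.025 |
| 0.25 | 1.436 | 0.285 | 1.118 | 0.185 |
| 0.5 | 2.872 | 0.795 | 2.236 | 0.564 |
| 0.75 | 4.308 | 0.987 | 3.354 | 0.889 |

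For a between-group t-test on change, the common rise cancels. In 40,000 simulated trials at each common rise of 0, 0.5, 0.75 and 1.0 SD, with 33 versus 14 and 33 versus 20 patients, the test favoured BFR in 2.4% to 2.6% of trials.

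**Step 4. What the between-group contrast can detect.** With 33 BFR patients and 14 prospective controls, √(1/33 + 1/14) = 0.319.

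- Difference detectable with 80% power: (1.960 + 0.842) × 0.319 = 0.89 SD.
- Power for a 0.5 SD difference: Φ(0.5/0.319 − 1.960) = Φ(−0.39), or about 35%.

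Study Design also mentions 20 controls. With 33 versus 20, the same formulas give 0.79 SD and about 42%.

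**The case against.** The strongest reply is that this is loose wording in one secondary hypothesis of a self-described pilot, and that the rest of the plan already points to a comparison. Circumference is listed in the visit schedules that follow the heading Functional Outcome Definitions/Data Points Collected, beside the step-down, balance and hop tests. The t-test sentence does not name those tests either, yet primary hypothesis 2a requires a control comparison for them. On that reasoning, outcome variables should include circumference too. This is a fair reading, and it is why the analysis section is ambiguous rather than clearly deficient. It does not mend 2a, whose wording would still be met by a rise over time whatever the t-test showed.

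A reader might go further and infer that the plan will run a within-group test and report any rise as a BFR effect, or that the false-claim rate is inflated by a known amount. The documents do not support either inference. No paired test is specified, no SD or expected rise is given, and a correction for multiple comparisons is promised. The rises in the illustration are assumed, and a fall from pre-operative to 3 months would push the other way. Nor do the documents support saying that recovery and growth would confirm 2a; they could, depending on the time points.

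Two further points stand. Both limbs are measured, so a reference for symmetric growth is already in the data, although no index uses it. And the 2.5% rate for the between-group test assumes equal natural change in groups that are not randomised; the prospective controls are treated at other facilities.

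**Conclusion.** The mismatch between secondary aim 2 and hypothesis 2a is real and should be corrected. As worded, 2a tracks change over time, in either direction, and not the effect of adding BFR. The analysis section does not clearly supply the missing comparison.

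The size of the problem cannot be fixed from the documents. In 33 patients, a natural rise of about half an SD of the change score would be enough to satisfy a within-group version of 2a four times in five with no BFR effect. A quarter of an SD would do so a little more than one time in four. These figures rest on the assumed rises and on a paired test that the plan does not itself name, so they show sensitivity and are not an estimate of error in this study. The flaw lies in the hypothesis and the analysis wording. Circumference is already to be collected in the prospective controls.

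**What to change.** 1. Reword hypothesis 2a as a greater change in the BFR group than in controls between named time points. State the measure: involved-limb circumference or, preferably, the involved-minus-uninvolved difference, which removes symmetric growth and uses measurements already planned.
2. In Data Analysis, name mid-thigh circumference among the variables compared between the BFR and non-BFR groups, and label within-group change over time as descriptive only.
3. Say which contrast applies to which controls. For prospective controls, use change from pre-operative to 3 months and to return to sport. If retrospective controls are used, compare levels at 3 months and at return to sport, or the change between those two visits, because no pre-operative assessment is named for them.

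The cost is a few sentences, with no new data for BFR patients and prospective controls. The price is power: about 35% for a 0.5 SD difference with 33 versus 14 patients before any multiplicity correction, which the plan should state. Because the groups are not randomised, the contrast removes common recovery and growth but not confounding, and the result should be described accordingly.

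### Secondary hypothesis 2a predicts a rise in thigh circumference over time with no control group, so recovery or growth could satisfy it without any BFR effect

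*Combined protocol and SAP*

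**What the plan says.** Under Secondary aim, aim 2 is "To determine the impact of adding BFR training during post-surgical rehabilitation on hypertrophy and mid-thigh circumference". That is a question about the effect of an addition, so it needs a comparison with patients who did not receive it. Hypothesis 2a is that "BFR training will demonstrate significant increased mid-thigh circumference over measured time points". It refers to time points and to no other group.

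Two sibling hypotheses do name the comparison. For function (primary 2a): "BFR training will improve scores on lower extremity functional tests when compared to a control group". For patient-reported outcomes (secondary 1a): "BFR training will show greater patient reported outcome scores on the post-op when compared to a control group".

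Circumference is recorded before surgery, at 3 months and at return to sport. The pre-operative item reads "Measured at 10cm above the superior pole of the patella bilaterally", and the two later visits repeat it. Item 7 of the data-points list says prospective controls supply the same data.

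The Data Analysis section plans descriptive statistics for "lower extremity strength, mid-thigh circumference and outcome measures". Its next sentence plans "T-tests between strength and outcome variables for the BFR and non-BFR group". It adds correlation tests and an unspecified multiplicity correction. It names no change-score, repeated-measures or group-by-time analysis.

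**The concern.** On its plain reading, 2a is met if thighs in the BFR group are larger later than earlier. BFR is not the only thing that can do that. Participants are 12 to 18 years old, so some may still be growing; skeletal maturity is recorded but no adjustment for it is planned. The Background describes progressive lower-limb strengthening as part of standard care without BFR. A significant rise could therefore be reported as hypertrophy due to BFR when controls rose just as much.

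The error can also run the other way. If circumference falls after surgery, BFR might reduce the loss without producing a net increase. Hypothesis 2a would then fail although BFR helped. Both errors come from the missing comparator, and because 2a does not say which interval counts, the plan does not show which is the more likely.

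**Working it through.** **Text check.** The plan states no SD, effect size, alpha or power for circumference, so there is no figure of its own to reproduce.

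| Item | Comparator in the hypothesis? | Side-to-side index defined? | Named for the between-group t-tests? |
|---|---|---|---|
| Strength | No: an association with BFR (primary 1a) | Yes, a deficit | Yes |
| Functional tests | Yes (primary 2a) | For reach and hop tests | Only through the general term for outcomes |
| Patient-reported outcomes | Yes (secondary 1a) | Not applicable | Through the general term for outcomes |
| Thigh circumference | No (secondary 2a) | No, though both thighs are measured | Unclear: listed apart from outcomes in the descriptive sentence, not named in the t-test sentence |

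**Illustration.** Inputs:

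- BFR group of 33, and 14 prospective controls (Study Design).
- 20 patients with one-year follow-up, as a smaller case (Data Analysis).
- Assumed, not in the documents: two-sided 5% without multiplicity correction, normally distributed change, zero BFR effect, and a natural gain d of 0.25, 0.5 or 0.75 SD of within-person change.

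*Within-group test.* The chance of a significant increase is P(T > t_crit), where T is noncentral t with n − 1 degrees of freedom and noncentrality d√n.

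| n | t_crit | d = 0.25 | d = 0.5 | d = 0.75 |
|---|---|---|---|---|
| 33 (√33 = 5.745) | 2.037 | noncentrality 1.44: 29% | 2.87: 80% | 4.31: 99% |
| 20 (√20 = 4.472) | 2.093 | 1.12: 19% | 2.24: 56% | 3.35: 89% |

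*Between-group t-test on change, 33 versus 14.* A gain shared by both groups cancels. In 40,000 simulated trials per setting the rejection rate was 4.9% to 5.1% at every natural gain tried, from 0 to 1.0 SD.

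*Opposite direction.* Suppose circumference naturally falls by 0.5 SD and BFR adds 0.5 SD. The net change is −0.5 + 0.5 = 0, so a within-group test finds a significant increase only 2.5% of the time despite a real benefit. The between-group test has about 34% power for that benefit: noncentrality 0.5 × √(33 × 14 / 47) = 0.5 × 3.135 = 1.57, t_crit 2.014.

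*Precision of a between-group test.* At 80% power, 33 versus 14 detects about 0.91 SD of change (0.91 × 3.135 = 2.85). With 33 versus 20 it is about 0.81 SD (0.81 × √(660/53) = 0.81 × 3.529 = 2.86). With 33 versus 14, power at 0.8 and 1.0 SD is about 69% and 87%.

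**The case against.** The strongest reply is that the comparison is already there. Aim 2 is comparative, controls are measured the same way, and the term outcome variables in the t-test sentence can be read broadly. It has to be: the hop, balance and step-down tests are not named in the Data Analysis section either, yet primary 2a requires comparing them with controls, so they can enter only through that term. Circumference sits in the same list of collected data points.

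Much of this stands. A reader might infer that circumference is definitely left out of the between-group tests, or that a paired test in the BFR group is planned. The documents support neither. The first turns on an ambiguous phrase and the second appears nowhere, so the percentages above describe a test that the plan does not contain. The size of the natural change is assumed, and over the first 3 months even its sign is uncertain. The illustration also ignores the promised multiplicity correction.

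What does not stand is that this settles the matter. Even if circumference is among the t-tests, 2a remains a claim about change over time. No analysis of change is specified, no visit is chosen from the three, and no side-to-side measure is defined. Hypothesis and analysis do not match on either reading.

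It is also fair that this is one secondary hypothesis in a self-described pilot whose Study Limitations already concede sampling bias and small numbers. That limits the weight of the point but does not answer it.

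**Conclusion.** The point holds as a fault in how the hypothesis is stated and matched to an analysis. As worded, 2a can be met with no BFR effect and can fail when there is one, so it does not answer aim 2. This rests on the text alone.

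The size is illustrative. Under the assumed gains, a within-group reading would be significant 29% to 99% of the time with 33 patients and 19% to 89% with 20, against about 5% for a between-group contrast. Those figures depend on the assumed gain being positive and of that order.

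It would be too strong to say that a between-group contrast would isolate the BFR effect. Prospective controls have their therapy at other facilities, so therapy site and BFR are confounded whichever test is used. This should be corrected, but it does not threaten the primary aims.

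**What to change.** Restate 2a as a between-group hypothesis: the involved-minus-uninvolved thigh circumference differs between BFR and control patients at one named visit (3 months or return to sport), adjusted for the pre-operative difference. Name that analysis in the Data Analysis section, for example as a regression on group and the pre-operative difference. Both thighs are already measured at all three visits in BFR patients and prospective controls, so no new data are needed.

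The costs and limits should be stated with it:

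- **Precision.** With 33 versus 14, only a difference of about 0.91 SD of change is detectable at 80% power (unadjusted t-test on change). An estimate with a confidence interval will say more than a p-value.
- **Retrospective controls.** Item 8 of the data-points list gives them 3-month and later assessments but no pre-operative one. If they are used, that comparison would have to be unadjusted and rely on the side-to-side difference, and the plan should say so.
- **The uninvolved thigh.** It reduces the influence of growth and body size but does not remove it, and it may itself respond to training, since the programme includes bilateral exercise. It does not account for recovery of the operated leg, so the control group is still needed.
- **Therapy site.** Confounding by site remains and belongs in the Study Limitations section.

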- 6. 12-month testing

Tegner Activity Scale

- 7. Prospective control: All prospective controls will follow the ACL reconstruction protocol at an outside facility. These patients will complete outcome measures, and standardized strength assessments consistent with the standard current standard of care listed above. The same data points will be collected.
- 8. Retrospective controls: Outcome measures (RSI, IKDC) and the results of standardized 3 and 6mo + assessment results will be collected.
- 9. All data points listed above for all three groups will be stored in a Microsoft Excel spreadsheet on the G drive.

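### The protocol sets out to determine the safety of adding BFR, but with no adverse-event data from controls and no reference rate it can only describe tolerability

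*Combined protocol and SAP*

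**What the plan says.** - **Purpose.** Under Purpose of the Research, Specific Aims and Hypotheses, the study is to "determine the safety and efficacy regarding the addition of BFR-based exercise to traditional methods of physical therapy".
- **Hypothesis.** Secondary aim 3 is to determine and record tolerance and side effects. Its hypothesis, 3a, is: "We hypothesize that patient tolerance to BFR will be consistent with previously published literature".
- **Benchmark.** Previous Work describes the safety literature only in words: side effects are minimal, and the risk is no greater than with traditional methods. It cites sources [10] to [13] but gives no rate. The Background adds that "there is limited information about the use of BFR in the adolescent population".
- **BFR group data.** At the end of Proposed Protocol, exertion and ability to complete are recorded after each exercise, and side effects after each session using the categories of a cited 2018 review.
- **Control data.** Prospective controls have therapy at an outside facility and supply the same data points as those listed in Patient Reported Outcomes and in the assessment lists. Those lists contain questionnaires, strength, circumference and functional tests, and no adverse events. Retrospective controls supply RSI, IKDC and assessment results.
- **Analysis.** Data Analysis plans descriptive statistics for "the effect of BFR training on lower extremity strength, mid-thigh circumference and outcome measures", then t-tests and correlations on strength and outcome variables. It does not mention side effects, exertion, completion or tolerance.

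**The concern.** The safety of adding BFR to standard rehabilitation is a question of contrast: which events occur with BFR beyond those that follow ACL reconstruction anyway? Pain, numbness, thrombosis and re-injury can occur after this surgery with or without a cuff. If events are recorded in one group only, they cannot be attributed to BFR, and BFR cannot be cleared of them.

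Hypothesis 3a replaces the concurrent contrast with a comparison to published experience. It does not say which rate, for which event, or how far from it counts as inconsistent. In a small sample, a failure to stand out from the literature could then be reported as evidence of safety in adolescents, a population for which the protocol itself says information is limited.

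**Working it through.** The documents give no event rate, margin, power or sample size for tolerance, so there is no planned figure to reproduce. The check asks what the planned numbers could show.

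**Inputs**
- BFR patients: 33 (Study Design).
- Prospective controls: 14 (Study Design; the same section also mentions 20 when it introduces the retrospective fallback).
- Study endpoint: 20 patients with one-year follow-up (Data Analysis). The group is not specified; 20 is used below as a low case in which all are BFR patients.
- Benchmark rates: none in the documents. Values from 1% to 30% are assumptions, for illustration.

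**1. What zero events would exclude.** The upper limit of the exact two-sided 95% interval for 0 of n is 1 − 0.025^(1/n).
- n = 33: 1 − 0.025^(1/33) = 10.6%
- n = 20: 1 − 0.025^(1/20) = 16.8%

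**2. Chance of seeing an uncommon event at least once**, at an assumed true risk of 1% per patient: 1 − 0.99^n.
- n = 33: 1 − 0.99^33 = 28%
- n = 20: 1 − 0.99^20 = 18%

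**3. Precision when events do occur** (Clopper-Pearson 95% interval, n = 33).
- 3 of 33 (9.1%): 1.9% to 24.3%
- 5 of 33 (15.2%): 5.1% to 31.9%

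**4. What a formal rule would achieve.** Suppose a benchmark p0 were stated, and consistency were rejected at the smallest count r with P(X ≥ r | 33, p0) ≤ 0.05. Power against a doubled rate is P(X ≥ r | 33, 2·p0).

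| Assumed p0 | Reject at | Power if the true rate is 2·p0 |
|---|---|---|
| 1% | ≥ 2 patients | 14% |
| 5% | ≥ 5 | 23% |
| 10% | ≥ 7 | 50% |
| 20% | ≥ 12 | 72% |
| 30% | ≥ 15 | 97% |

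A doubling of a common side effect would usually be noticed; a doubling of an uncommon one would usually be missed. The plan sets neither a benchmark nor a rule.

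**5. What a control comparison could add.** If events were collected in both groups, 33 against 14 would give about 28% power for 30% against 10% (assumed rates, two-sided 5%). The comparison would be descriptive, not a test.

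**The case against.** The strongest defence is that this is the third secondary aim of a declared pilot. It is worded as determining and recording tolerance, and Study Limitations admits the small sample. Collection in BFR patients is properly specified. The literature is not anonymous: sources [10] to [13] are cited, and side-effect recording is tied to the 2018 review. All of this stands, and it supports a descriptive aim. It does not support the broader purpose of determining safety, which needs either a comparison or a stated reference.

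Three stronger readings are tempting but are not supported:

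- *Tolerance data never reach the study data set, or become unlinkable.* A reader might infer this because exertion goes to a flow sheet and side effects to the chart, while item 9 after 12-month testing says "All data points listed above for all three groups will be stored in a Microsoft Excel spreadsheet on the G drive", and the tolerance items come later. But Identification and Recruitment sends information listed in the protocol to a data collection sheet, and Data Collection and Management says all data go into Excel. The sheet is an attachment not available here. Human Subjects Protections keeps record numbers for linkage and de-identifies only after all data are collected.
- *No result could contradict hypothesis 3a.* The table above shows that a marked excess of a common side effect would be visible in 33 patients, and investigators could call it inconsistent. What is missing is any rule that would require them to.
- *Counting sessions would overstate safety by a factor of about 23.* Zero events in 33 × 24 = 792 sessions gives a limit of 0.46%, but per session. Over 24 independent sessions, 1 − 0.025^(24/792) = 1 − 0.025^(1/33) = 10.6%, the same per-patient limit. The plan does not propose a session denominator in any case.

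A fair warning also applies to any remedy. BFR patients are observed after every session, whereas controls would be asked to recall events at a few visits. Setting those two side by side would inflate the apparent harm of BFR.

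**Conclusion.** The point holds in a limited form. Followed as written, the plan can describe tolerance in BFR patients but cannot support a conclusion about the safety of adding BFR: controls supply no adverse events, hypothesis 3a has no reference rate or margin, and the analysis does not name tolerance. The missing benchmark and unnamed analysis would on their own be matters of detail. The one-sided recording is what limits the conclusion.

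Even a clean result, with no events in 33 patients, is compatible with a true per-patient risk of up to 10.6% (16.8% in 20). An event with a true 1% risk would be missed altogether 72% of the time (100% − 28%).

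These figures assume that patients are independent and that all 33 recruited BFR patients contribute. The Retention rule, which requires attendance at 90% of visits for inclusion, could reduce that number and might remove patients who stop because they tolerate BFR poorly. That control events are absent rests on the listed data points; the phrase saying the same data points will be collected does not naturally extend to items recorded at BFR sessions. The term outcome measures in Data Analysis could be stretched to tolerance, but Patient Reported Outcomes uses it for the four questionnaires.

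**What to change.** 1. **Purpose and aim 3.** In the purpose statement, replace determining safety with describing tolerability. Replace hypothesis 3a with a descriptive objective: per BFR patient, the proportion with each side effect and the proportion unable to complete sessions, each with an exact 95% confidence interval. Name this summary in Data Analysis, and state that risks below about 10% cannot be excluded even if no event is seen.
2. **Same questions for both groups.** Ask BFR patients and prospective controls an identical short set of event questions at the existing 3-month, return-to-sport and 12-month assessments. Compare the groups descriptively on those answers only. Report the session-by-session BFR recording separately, because more frequent observation finds more events.

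**Cost.** Protocol wording, a few questions at existing assessments, and columns for the answers. The strength and functional analyses are unaffected. The downsides are a more modest safety claim, an imprecise comparison (33 against 14), and no such data for any retrospective controls, so a comparison that falls back on them would have no event data on the control side.
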